3.14 Pathologic Stage T0-T3N0-N1M0. (8th edition)
3.15 ECOG Performance Status (PS) 0 to 2. (Appendix I).
3.16 Able to and provides IRB approved study specific written informed consent.
3.17a Study entry (randomization) must be within 12 weeks of last surgery (breast or axilla) or last chemotherapy (if applicable).

- 3.17b Willing to return to enrolling institution for follow-up (during the active monitoring phase of the study).
- 3.18 Fair, good or excellent cosmesis, as determined by trained nurse assessment using the Harvard Cosmetic Scale.
- 3.19 Radiotherapy must begin within 12 weeks of the last breast cancer surgery or the last dose of adjuvant chemotherapy.
- 3.20 Breast conserving surgery and indications for whole breast radiotherapy.

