16.0 Statistical Considerations and Methodology

- 16.1 Overview: This is an open label phase III randomized controlled trial to determine the safety of 5 fraction vs 15 fraction radiotherapy after breast conserving surgery. The goal is to determine whether the difference in 24-month complication rates between the experimental arm and the control arm is acceptable. Of interest is whether the experimental arm results in an unacceptable increase in the 24-month complication rate. If it does not, then the experimental arm will be recommended for further study. If the 24-month complication rate is found to be unacceptable, then the recommendation would be to do no further studies of the experimental arm.

- 16.2 Primary and Secondary Endpoints

16.21 Primary Endpoint: The 24-month complication rate, defined as the percentage of women evaluable at 24 months who develop one or more of the following events:

- 1) grade 3 or higher late adverse event OR
- 2) deterioration of cosmesis from excellent/good to fair/poor or from fair to poor at the 24-month evaluation (using the Harvard/NSABP/RTOG Cosmesis Scale)

16.22 Secondary Endpoints:

16.221 Acute and late adverse events including grade ≥ 2 pneumonitis.

16.223 Locoregional control, invasive disease-free, distant recurrence, disease-free survival, cause-specific survival, overall survival.

The following definitions are used for the secondary endpoints of interest:

- *Acute adverse events*: any adverse event, regardless of attribution, that occurs in the first 90 days post-RT.
- *Late adverse events* (up to 5 years post RT): any adverse event that occurred after the first 90 days post-RT and up to 5 years post-RT.
- *Ipsilateral breast tumor recurrence (IBTR)*: this is defined as local recurrence from trial registration as a first event at 5 years. IBTR is defined as both invasive and non-invasive breast cancer involving the same breast parenchyma as the original tumor.
- *Regional recurrence*: invasive breast cancer in the axilla, regional lymph nodes, chest wall, and skin of the ipsilateral breast at 5 years.
- *Distant recurrence*: metastatic cancer that has either been biopsy confirmed or clinically diagnosed as recurrent invasive breast cancer at 5 years.

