- *Invasive disease-free survival*: this is defined as the time from study registration until the occurrence of one of the events in a composite endpoint. This endpoint includes invasive IBTR, regional invasive breast cancer recurrence, distant breast cancer recurrence, death due to any cause.
- *Disease-free survival*: this is defined as the time from study registration until the occurrence of one of the events in a composite endpoint. This endpoint includes any IBTR, regional invasive breast cancer recurrence, distant breast cancer recurrence, death due to any cause,
- *Cause specific survival*: is defined as the time from registration to death due to breast cancer. If the cause of death is unknown or difficult to establish patients with a distant failure at the time of death would be censored as dying from breast cancer
- *Overall survival*: is defined as the time from registration to death due to any cause.

16.3 Exploratory endpoints:

16.31 Patient self-reported cosmesis evaluate fatigue, breast pain, arm function and other patient reported outcomes.

The following definitions are used for the exploratory endpoints of interest:

- *Patient Reported Outcomes/Quality of life:* Elements of the Patient-Reported Outcomes Version of the Common Terminology Criteria for Adverse Events (PRO-CTCAE) will be used for patient self-reporting of toxicities. The Breast Cancer Treatment Outcomes Scale (BCTOS) will be used to measure patient reported functional status (pain, mobility). Other measures of fatigue, pain, and arm function are listed in the appendix.
- *Patient self-reported cosmetic outcomes:* the patient self-reported outcome will be assessed using a modified Harvard Cosmesis Scale and the BCTOS at baseline, 2 years, and 5 years.
- *Panel assessed cosmetic outcome:* in addition to patient self-reported and physician reported outcomes, cosmesis will be assessed by a panel of breast cancer medical providers using digital photographs from baseline and at 2 years. The Panel will be blinded to treatment allocation.

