16.4 Sample Size Determination

This study requires 100 evaluable women for the primary endpoint analysis (50 evaluable patients per arm).

Ninety-two percent of expected patients completed a 3-year assessment of cosmesis in the randomized phase III study reported by Olivotto et al.⁶¹ Expected was defined as patients who were projected to have had their 3-year follow-up visit based on the date of random assignment and who did not experience recurrence, undergo mastectomy, or die. Therefore to be conservative we will anticipate enrolling 10 (5 per arm) additional patients to account for ineligibility, cancellation, major treatment violations, or other reasons. The maximum projected enrollment is therefore 110 women.

In a large randomized controlled trial Whelan and colleagues compared cosmetic outcomes between conventional and hypofractionated whole breast radiotherapy after lumpectomy. At baseline, 84% of patients in the hypofractionated arm were rated as having good or excellent cosmesis by trained nursing assessment. At 3 years, the percentage was 77%, or an absolute change of 7%.⁶² In the study proposed here, a subset of patients may receive a boost to the lumpectomy cavity which has been associated with a slightly higher risk of fibrosis and adverse cosmesis.^{63,64} Therefore, the sample size proposed for arms 1-2 is based on an assumed value of a 10% complication rate in the control arm. The rate of grade 3 or higher late toxicity in this population is expected to be $\leq 1\%$ (Whelan ASCO 2011). Since the local failure rate and death rate at 2-years in the UK start B trial²⁴ was less than 3% we assume that an additional 10% to account for patients lost to follow, failures, deaths and others should be adequate (Total enrollment of 110 patients).

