points along with 95% CIs. Comparison between arms will employ a log-rank test.

16.627 *Overall survival:* The OS will be estimated with a Kaplan-Meier estimator and curve by treatment arm. Estimates will be given for specific time points along with 95% CIs. Comparison between arms will employ a log-rank test.

16.631 *Quality of life:* The subscales of the BCTOS, elements from CTCAE-PRO, and other patient reported measures such as fatigue, breast pain, breast shape, and arm related morbidity outlined in the appendix will be summarized as the mean \pm SD and median (minimum value, maximum value). Mixed models will be used to estimate changes at fixed time points as well as compare outcomes between arms.

16.632 *Cosmesis:* The values of the cosmesis instruments (patient self-reported and panel-assessed) will be summarized with the frequencies and confidence intervals of fair or poor cosmesis events at baseline, 2 years, and 5 years by treatment arm. Comparisons between arms will employ chi-squared tests.

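### Section 16.632 compares exploratory patient-rated and panel-rated cosmesis without using each woman's baseline rating; the test is valid but gives up precision that is cheap to recover

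*Combined protocol and SAP*

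**What the plan says.** - **Analysis.** Section 16.632 tabulates "frequencies and confidence intervals of fair or poor cosmesis events at baseline, 2 years, and 5 years by treatment arm" for the patient and panel instruments, then states: "Comparisons between arms will employ chi-squared tests". It names no baseline covariate, stratum or change score.
- **Status.** Section 16.632 stands below the heading of 16.62, which covers secondary analyses. But 16.3 introduces both ratings with "The following definitions are used for the exploratory endpoints of interest", and the secondary list in 16.22 does not contain cosmesis. They are exploratory.
- **Time points.** In 16.3 the patient rating uses a "modified Harvard Cosmesis Scale and the BCTOS at baseline, 2 years, and 5 years". The panel rates cosmesis "using digital photographs from baseline and at 2 years", with no 5-year panel rating. Section 16.632 lists 5 years for both.
- **Baseline variation.** Criterion 3.18 admits women with "Fair, good or excellent cosmesis, as determined by trained nurse assessment using the Harvard Cosmetic Scale". Section 5.0 stratifies on treatment modality, to which 6.21 adds the registering membership. Baseline cosmesis is not a factor.
- **Handling elsewhere.** The cosmesis part of the primary endpoint (16.21) is "deterioration of cosmesis from excellent/good to fair/poor or from fair to poor at the 24-month evaluation". Section 16.631 uses mixed models to estimate change in the BCTOS subscales and other patient-reported measures.

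**The concern.** A woman who starts fair and stays fair counts as a fair/poor event at 2 years although nothing has changed. The primary endpoint would not count her. The two cosmesis analyses therefore answer different questions, and 16.632 makes no use in its test of a baseline value that the plan already provides for.

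Two things are at stake. First, if the baseline rating predicts the later one, an unadjusted test is less precise than it could be, with only about 50 women per arm. Second, because allocation does not balance baseline cosmesis, a chance imbalance shows up as part of the observed difference at follow-up. This matters most for the panel, the only cosmesis rating that the plan describes as blinded in an open-label trial.

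**Working it through.** **Plan's own figure.** The plan gives no sample size or power for 16.632. The primary one (16.5) reproduces: n per arm = (1.645 + 0.842)² × 2 × 0.10 × 0.90 / 0.15² = 49.5, so 50. Power at 50 per arm is Φ(0.15/0.06 − 1.645) = 80.4%. I use 50 per arm below.

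**Inputs.**
- Baseline fair/poor: 16%. Section 16.4 says of a cited trial: "At baseline, 84% of patients in the hypofractionated arm were rated as having good or excellent cosmesis", and 100 − 84 = 16.
- Follow-up fair/poor: 100 − 77 = 23%, from the 3-year figure in 16.4.
- Both are nurse ratings from one arm of that trial, used here as stand-ins for patient and panel ratings.
- Persistence s, the probability of fair/poor at follow-up given fair/poor at baseline, is not in the documents. It is an assumption, varied from 0.4 to 0.9.
- The test level is assumed to be two-sided 5%; 16.632 states none.

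**Formulas.** The rate among women excellent/good at baseline is w = (0.23 − 0.16s)/0.84. The variance per woman is 0.23 × 0.77 = 0.1771 without adjustment and 0.16·s(1−s) + 0.84·w(1−w) within baseline strata.
- s = 0.4: w = 0.198, within-stratum variance 0.1716, ratio 0.97.
- s = 0.9: w = 0.102, within-stratum variance 0.0916, ratio 0.52.

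**Simulation.** 200,000 trials per scenario compared the unadjusted chi-squared test with a Cochran-Mantel-Haenszel test and Mantel-Haenszel risk difference stratified by baseline (excellent/good vs fair/poor). Variance ratios are adjusted over unadjusted, with no true effect. Power is for a 15-point increase in both strata.

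| s | Variance ratio | Power, unadjusted | Power, stratified |
|---|---|---|---|
| 0.4 | 0.976 | 37.2% | 37.7% |
| 0.5 | 0.927 | 37.1% | 39.1% |
| 0.6 | 0.856 | 37.0% | 41.1% |
| 0.7 | 0.764 | 37.2% | 44.6% |
| 0.8 | 0.658 | 37.1% | 49.1% |
| 0.9 | 0.525 | 34.0% | 50.8% |

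At s = 0.9 the rate in the fair/poor stratum cannot exceed 100%, so the average increase there is 0.84 × 15 + 0.16 × 10 = 14.2 points. That is why unadjusted power dips in the last row.

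**Chance imbalance.** The SD of the baseline difference is √(2 × 0.16 × 0.84/50) = 7.3 points. The exact probability of a difference of 5 or more women (10 points), in either direction, is 22%. With no treatment effect, a 10-point imbalance shifts the expected unadjusted difference by 10 × (s − w) points: 10 × (0.4 − 0.198) = 2.0 at s = 0.4, and 10 × (0.9 − 0.102) = 8.0 at s = 0.9. The simulation gave 2.2 and 7.9, with the stratified estimate between −0.1 and 0.2 points across all values of s.

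**Error rate.** Over all randomisations with no effect, the chi-squared test rejected in 5.0% to 5.1% of trials. In trials with exactly that 10-point imbalance it rejected in 5.6% to 8.0%, against 4.6% to 5.2% for the stratified test.

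**The case against.** The case for leaving 16.632 alone is respectable. The endpoints are exploratory, with no alpha, power or decision attached. An unadjusted comparison of randomised arms is valid. Baseline is tabulated by arm, so a reader would see an imbalance. Patient-reported change is partly covered by the mixed models in 16.631. The benefit rests on an association that nobody has stated, and at 40% persistence it is negligible. Even with adjustment, power in these scenarios does not exceed about 51%.

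Most of this limits the size of the point without removing it. Tabulating baseline does not correct the test. The mixed models do not cover the panel rating or the Harvard-scale patient rating. Adjustment kept the level near 5% and did not lower power in any scenario run.

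Three stronger readings are tempting, and the documents do not support them.
- A reader might infer that baseline imbalance invalidates the test. It does not: overall type I error is not inflated, and the harm exists only conditionally on an imbalance.
- A reader might assume 80-90% persistence and conclude that adjustment is worth 1.5 to 1.9 times the sample (1/0.658 and 1/0.525). That is only the favourable end of an unknown range. The 16% may also include women rated poor, whom 3.18 excludes here on the nurse rating.
- A reader might treat the panel comparison as the plan's formal check on the nurse-rated primary endpoint. The plan gives it no such role.

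One practical objection stands. Footnote 3 of the test schedule (section 4.0) lets photographs be taken before or after treatment at the physician's discretion, so a pre-treatment panel rating may not exist for every woman.

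**Conclusion.** The point holds as one of efficiency and consistency in an exploratory analysis. Section 16.632 leaves the baseline rating out of a comparison in which it could help, while the primary endpoint and 16.631 both work from change. Under the assumed 16% and 23% rates, the gain from adjustment runs from almost nothing to nearly half the variance, depending on how strongly baseline predicts follow-up for these raters. Adjustment also removes the expected shift of roughly 2 to 8 points that a 10-point chance imbalance would otherwise produce. The primary analysis and its decision rule are not touched.

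**What to change.** In 16.632:
1. Replace the chi-squared test with a Mantel-Haenszel risk difference and confidence interval, and a Cochran-Mantel-Haenszel test, stratified by the same rater's baseline category. Use excellent/good vs fair/poor as strata, because 3.18 restricts only the nurse rating and a patient or the panel may rate a woman poor at baseline.
2. Apply this at 2 years for both ratings and at 5 years for the patient rating. Reconcile the panel time points between 16.3 and 16.632.
3. Also report deterioration from baseline by the 16.21 categories, noting how many women are rated poor at baseline and so cannot deteriorate further on that definition.
4. Use a panel baseline only where the photograph was taken before treatment. Keep women without one in the analysis through a missing-baseline category, and report their number by arm.
5. Label the analysis as exploratory, in line with 16.3.

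The cost is small. For the patient rating it is a change of wording and slightly more analysis work. For the panel, the benefit also relies on pre-treatment photographs being available.

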16.7 Data & Safety Monitoring

16.71 The study chair(s) and the study statistician will review the study at least twice a year to identify accrual, adverse event, and any endpoint problems that might be developing. The Mayo Clinic Cancer Center (MCCC) Data Safety Monitoring Board (DSMB) is responsible for reviewing accrual and safety data for this trial at least twice a year, based on reports provided by the MCCC Statistical Office.

16.72 Adverse Event Stopping Rules: The stopping rules specified below are based on knowledge available at study development. We note that the Adverse Event Stopping Rule may be adjusted in the event of either (1) the study re-opening to accrual or (2) at any time during the conduct of the trial and in consideration of newly acquired information regarding the adverse event profile of the treatment(s) under investigation. The study team may choose to suspend accrual because of unexpected adverse event profiles that have not crossed the specified rule below.

Accrual will be temporarily suspended if at any time we observe events considered at least possibly related to study treatment (i.e. an adverse event with attribute specified as “possible,” “probable,” or “definite”) that satisfy one of the following:

- If 4 or more patients in the first 10 treated patients (per treatment arm) experience a grade 3 or higher adverse event, besides acute dermatitis, at least possibly related to treatment at any time following completion of the protocol treatment within 90 days post-treatment.
- After the first 10 patients have been treated (per treatment arm): if $\geq 20\%$ of all patients experience a grade 3 or higher adverse event, besides acute

dermatitis, at least possibly related to treatment at any time following the completion of protocol treatment within 90 days post-treatment.

We note that we will review grade 4 and 5 adverse events deemed “unrelated” or “unlikely to be related”, to verify their attribution and to monitor the emergence of a previously unrecognized treatment-related adverse event.

16.8 Results Reporting on ClinicalTrials.gov: At study activation, this study will have been registered within the “ClinicalTrials.gov” website. The Primary and Secondary Endpoints (i.e., “Outcome Measures”) along with other required information for this study will be reported on ClinicalTrials.gov. For purposes of timing of the Results Reporting, the initial estimated completion date for the Primary Endpoint of this study is 48 months after the study opens to accrual. The definition of “Primary Endpoint Completion Date” (PECD) for this study is at the time the last patient registered has been observed for 24 months.

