10.0 Adverse Event (AE) Reporting and Monitoring

10.1 Definitions

Adverse Event- An untoward or undesirable experience associated with the use of a medical product (i.e. drug, device, biologic) in a patient or research subject.

Serious Adverse Event – Any grade 4 or 5 adverse event as defined by CTC AE v4.0.

Adverse events are classified as serious or non-serious. Serious problems/events can be well defined and include in general:

- Death
- Life threatening adverse experience where emergent lifesaving treatment is necessary.

Unanticipated Problems Involving Risks to Subjects or Others (UPIRTSO) - Any unanticipated problem or adverse event that meets the following three criteria:

Serious: Serious problems or events that results in significant harm, (which may be physical, psychological, financial, social, economic, or legal) or increased risk for the subject or others (including individuals who are not research subjects). These include: (1) death; (2) life threatening adverse experience; (3) hospitalization - inpatient, new, or prolonged; (4) disability/incapacity - persistent or significant; (5) birth defect/anomaly; (6) breach of confidentiality and (7) other problems, events, or new information (i.e. publications, DSMB reports, interim findings, product labeling change) that in the opinion of the local investigator may adversely affect the rights, safety, or welfare of the subjects or others, or substantially compromise the research data, **AND**

Unanticipated: (i.e. unexpected) problems or events are those that are not already described as potential risks in the protocol, consent document, not listed in the Investigator's Brochure, or not part of an underlying disease. A problem or event is "unanticipated" when it was unforeseeable at the time of its occurrence. A problem or event is "unanticipated" when it occurs at an increased frequency or at an increased severity than expected, **AND**

Related: A problem or event is "related" if it is possibly related to the research procedures.

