10.22 Assessment of Attribution

Only G4 or G5 adverse events will require an attribution. Any change in the grade of an adverse event within the list of monitored AEs will be recorded and considered to be related to treatment. Any new adverse not listed occurring within the Radiated area or in close proximity will be graded and attribution defined by the study PI.

Events determined to be possibly, probably or definitely attributed to a medical treatment suggest there is evidence to indicate a causal relationship between the treatment and the adverse event.

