10.3 Reporting of Serious Adverse Events and Unanticipated Problems

When an adverse event has been identified, the study team will take appropriated action necessary to protect the study participant and then complete the Study Adverse Event Worksheet and log. The sponsor-investigator will evaluate the event and determine the necessary follow-up and reporting required.

- a. Serious Adverse Events will be reported as part of regular adverse event reporting mechanisms via the data capture system and logged for review reporting.

10.31 Investigator Reporting: Notifying the Mayo IRB:

The IRB requirements reflect the guidance documents released by the Office of Human Research Protections (OHRP), and the Food and Drug Administration (FDA) in early 2007 and are respectively entitled “Guidance on Reviewing and Reporting Unanticipated Problems Involving Risks to Subjects or Others and Adverse Events” and “Guidance for Clinical Investigators, Sponsors, and IRBs: Adverse Event Reporting – Improving Human Subject Protection.”

10.311 According to Mayo IRB Policy any serious adverse event (SAE) which the Principal Investigator has determined to be a UPIRTSO must be reported to the Mayo IRB as soon as possible but no later than 5 working days after the investigator first learns of the problem/event.

10.312 Non-UPIRTSO – the investigator reports problems or events that do NOT meet criteria of an UPIRTSO in summary format at the

time of the next continuing review. The investigator monitors the severity and frequency of subsequent non-UPIRTSOs.

Consider the following information to collect when developing any forms for documentation of adverse events.

Example

Information collected on the adverse event worksheet (and entered in the research database):

- Subject's name:
- Medical record number:
- Disease/histology (if applicable):
- The date the adverse event occurred:
- Description of the adverse event:
- Relationship of the adverse event to the research (drug, procedure, or intervention):
- If the adverse event was expected:
- The severity of the adverse event: (use a table to define severity scale 1-5)
- If any intervention was necessary:
- Resolution: (was the incident resolved spontaneously, or after discontinuing treatment)
- Date of Resolution:

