The investigator will review all adverse event reports to determine if specific reports need to be made to the IRB and FDA. The investigator will sign and date the adverse event report when it is reviewed. For this protocol, only directly related SAEs/UPIRTSOs will be reported to the IRB.

10.4 Adverse events to be graded at each evaluation and pretreatment symptoms/conditions to be evaluated at baseline per the CTCAE v5.0 grading unless otherwise stated in the table below. Version 4 is allowed if v5 is not available, however, AEs will have to be updated to V5 once is available:

System (SOC)	Organ Class	Adverse event/Symptoms	Baseline	Each evaluation	Grading scale (if not CTCAE)
General		Pain	X	X	CTCAE
Skin and subcutaneous tissue disorders		Dermatitis Radiation	X	X	CTCAE
		Skin hyperpigmentation	X	X	CTCAE
		Skin hypopigmentation	X	X	CTCAE
		Superficial Soft Tissue Fibrosis	X	X	CTCAE
		Breast edema (lymphedema)	X	X	CTCAE

Vascular	Lympedema -arms	X	X	CTCAE
Respiratory, thoracic and mediastinal disorders	Pneumonitis	X	X	CTCAE

10.5 Submit via appropriate *reporting mechanisms* the following AEs experienced by a patient and not specified in Section 10.4:

- 10.52 Grade 3, 4, and 5 AEs regardless of attribution to the study treatment or procedure.
- 10.53 Grade 5 AEs (Death)
- 10.531 Any death within 30 days of the patient's last study treatment or procedure regardless of attribution to the study treatment or procedure
- 10.532 Any death more than 30 days after the patients last study treatment or procedure that is felt to be at least possibly treatment related must also be submitted as a Grade 5 AE, with a CTCAE type and attribution assigned.

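### The accrual-suspension rule exempts acute dermatitis at every grade, so related grade 4-5 dermatitis never counts toward the only mandatory pause; capping the exemption at grade 3 is a minor, cheap improvement

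*Combined protocol and SAP*

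**What the plan says.** Section 16.72 has two bullets that oblige a temporary suspension of accrual. The first is met when 4 or more of the first 10 treated patients in an arm "experience a grade 3 or higher adverse event, besides acute dermatitis, at least possibly related to treatment" within 90 days after treatment. The second applies after the first 10 patients, uses a 20% threshold, and carries the same exemption. Neither bullet limits the exemption by grade.

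Elsewhere the plan treats severe events as serious whatever the organ. Section 10.1 defines a serious adverse event as "Any grade 4 or 5 adverse event as defined by CTC AE v4.0". Section 10.4 puts "Dermatitis Radiation" on the list graded at baseline and at each evaluation, and section 10.22 says that any "change in the grade of an adverse event within the list of monitored AEs will be recorded and considered to be related to treatment".

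Section 16.72 also has softer provisions. The rule may be adjusted "at any time during the conduct of the trial and in consideration of newly acquired information regarding the adverse event profile", and "The study team may choose to suspend accrual because of unexpected adverse event profiles that have not crossed the specified rule below". It closes by saying that "we will review grade 4 and 5 adverse events deemed “unrelated” or “unlikely to be related".

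**The concern.** Exempting grade 3 dermatitis is defensible. Section 9.0 calls skin changes common, and an expected in-field reaction should not halt accrual. The wording goes further and also removes grades 4 and 5, for which the plan gives no reason. Read literally, 10 of 10 patients in an arm could have related grade 4 dermatitis without meeting either bullet.

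The closing grade 4-5 review does not bring these cases back. It covers events judged unrelated or unlikely to be related, whereas section 10.22 makes a grade change in a monitored event related by default.

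The argument for a cap is uncertainty rather than a known skin hazard. Section 1.3 says there are no data on hypofractionated scanning-beam protons for breast cancer, and section 1.4 says the proton RBE may differ from 1.1. That reasoning reaches only the proton patients, at most 28 per arm (section 5.0). If the 5-fraction proton regimen were unexpectedly harsh on skin, severe dermatitis alone could not trigger the mandatory pause. Other related grade 3 or higher events would still count.

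**Working it through.** **Does anything else oblige a pause?** Each alternative route, with what it requires:

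- Suspension by the study team and adjustment of the rule (16.72): permitted, not required.
- Grade 4-5 review (16.72): a review of attribution, for events called unrelated or unlikely.
- Study team and DSMB review (16.71): at least twice a year, with no dermatitis trigger.
- Event evaluation (10.3): "The sponsor-investigator will evaluate the event and determine the necessary follow-up and reporting required".
- UPIRTSO reporting (10.1, 10.311): within 5 working days. It can cover greater severity than expected, but it is reporting only.
- Termination considerations (16.5): adverse events are weighed.
- Section 8.0: no pre-specified interruptions.

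None is mandatory.

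**Size of the gap.** The plan gives no operating characteristics for the stopping rule, so there is no stated figure to reproduce. It also gives no grade 4-5 dermatitis rate, so the rates below are assumptions.

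Inputs: 55 patients per arm and at most 28 proton patients per arm (5.0); thresholds of 4 in 10 and 20% (16.72), with the 20% read per arm; assumed background b = 1% for other related grade 3 or higher events; assumed grade 4-5 dermatitis rate q.

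Probability that a patient counts:
- as written: p = b, whatever q is;
- with the cap, all 55 at risk: p = 1 − (1 − b)(1 − q);
- with the cap, protons only, spread evenly over accrual: p_mix = (28/55)p + (27/55)b.

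Example at q = 3%: p = 1 − 0.99 × 0.97 = 3.97%, and p_mix = (28/55) × 3.97% + (27/55) × 1% = 2.51%.

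Exact recursion, checked after each patient: let f_n(k) be the probability of k events after n patients with no crossing so far. Then f_n(k) = f_{n−1}(k)(1 − p) + f_{n−1}(k − 1)p. Remove and add up the states with k ≥ 4 for n ≤ 10, and those with k ≥ 0.2n for n from 11 to 55.

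Per-arm probability of a pause, b = 1%, second bullet from n = 11:

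| q | As written | Cap, protons only | Cap, all 55 |
|---|---|---|---|
| 1% | 0.043% | 0.141% | 0.316% |
| 3% | 0.043% | 0.614% | 2.21% |
| 5% | 0.043% | 1.59% | 6.54% |
| 10% | 0.043% | 6.81% | 28.8% |
| 20% | 0.043% | 29.9% | 84.2% |

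At 1% to 3% the gain is 0.141 − 0.043 = 0.10 to 0.614 − 0.043 = 0.57 percentage points for protons only, and 0.27 to 2.17 points if all 55 are at risk.

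**Sensitivity.**
- If the second bullet is also checked at n = 10, where 2 of 10 is already 20%, the as-written figure is 0.437%. The proton-only figures become 0.975% (q = 1%), 2.64% (3%), 13.8% (10%) and 39.6% (20%).
- With b from 0% to 2% (protons only, from n = 11), the ranges are 0.006-0.605% at q = 1%, 0.147-1.56% at 3%, 4.33-9.91% at 10% and 24.7-35.4% at 20%.
- Order of entry matters at the extremes. At q = 10%, treating all proton patients first gives 26.8%, and all last gives 0.09%.

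**Why the effect is small.** The thresholds are high. For dermatitis alone (b = 0), the chance of 4 or more in the first 10 is 0.001 at q = 5%, 0.013 at 10% and 0.121 at 20%. At n = 11 the 20% rule needs 3 events (3/11 = 27%).

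**Which rates are plausible?** Section 1.2 cites no acute grade 3 or higher skin toxicity in 100 partial-breast proton patients, a one-sided 95% upper bound of 1 − 0.05^(1/100) = 3.0%, and none in 12 post-mastectomy proton patients. Section 1.4 cites very low grade 3 rates with 26-27 Gy in one week. These settings differ from this trial. The bound concerns grade 3 or higher, of which grade 4-5 is only a part.

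**The case against.** The strongest reply is that the edit hardly works in the scenario that motivates it. At a 10% rate among 28 proton patients (28 × 0.10, about 3 expected cases), the amended rule still does not pause about 93% of the time. At 20% (5 to 6 cases) it does not pause about 70% of the time. Judgement would still decide in most such trials. That stands, and it is the main reason to rate the point low. A separate trigger on any related grade 4-5 dermatitis would be more sensitive: within the first 10 patients of an arm it would fire with probability 1 − 0.99^10 = 9.6% at a 1% rate. It would also pause the trial on a single case.

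The second reply is that the discretionary routes suffice in a trial of 110 patients. It stands in part. A reader might infer that severe dermatitis would go unseen. The documents do not support that: it is graded at each evaluation, needs an attribution at grade 4-5, is a serious event, and is open to team and DSMB review. What is missing is only the obligation to pause.

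A reader might also take the early partial-breast proton series in section 1.2, with high rates of acute skin toxicity, as evidence of a skin hazard here. The plan points to passive scatter and single-beam treatment as possible contributors and gives no grade. Section 1.2 says scanning beams may deliver less dose to skin.

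**Conclusion.** The wording gap is real: related grade 4-5 acute dermatitis contributes nothing to either bullet, and no other provision obliges a pause. Its consequence is minor. On the uncertainty argument, which covers proton patients only, closing the gap adds about 0.1 to 0.6 percentage points to the per-arm pause probability at dermatitis rates of 1% to 3%. If all 55 patients are equally at risk, it adds about 0.3 to 2.2 points. These figures assume a 1% background, checks from the 11th patient, a per-arm reading of the 20% and even mixing of modalities.

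It would be tempting to cite the 29% and 84% figures (10% and 20% rates in all 55 patients) as the size of the problem. Nothing in the documents supports rates of that order. Nor do the documents support reading this as a flaw that undermines the trial, or the exemption of grade 3 dermatitis as an error. It is an optional tightening of a safety rule.

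**What to change.** In both bullets of section 16.72, replace *besides acute dermatitis* with *besides grade 3 acute dermatitis*. Grade 4 or 5 dermatitis then counts like any other related grade 3 or higher event, and the exemption for the expected reaction stays.

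No new data are needed, because sections 10.4 and 10.22 already require the grading and the attribution. The cost is a slightly higher chance of a temporary pause. At a 1% rate in all patients (1% background), the per-arm chance rises from 0.04% to 0.3%, or from 0.4% to 1.7% if the second bullet is also checked at n = 10. For either of two arms, 1 − (1 − x)² gives 0.09% to 0.6%, or 0.9% to 3.3%.
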